6.2 Endpoints

Clinical study endpoints and associated definitions are listed in Table 3.

Table 3. COSTA clinical study endpoint definitions.

Endpoints	Definitions	
Primary	To evaluate the safety and tolerability of alvelestat administered twice daily (bid) for 5 or 10 days	
By treatment group (alvelestat/placebo):
 
 • Numbers and % of subjects who experience at least 1 treatment-emergent adverse event to Day 60 (Safety Outcome Assessment) • Adverse events of special interest (liver function abnormalities, corrected QT interval, infections, and neutropenia) and clinically significant safety monitoring labs tests to EoT • Number and % of subjects that discontinue alvelestat to Day 5 or 10 • Number and % of subjects requiring dose reduction to Day 5 or 10 • Number and % of subjects with AE of headache on prospective questioning and CTCAE severity Grade to Day 5 or 10 • Change in vital signs, EKG, safety laboratory measures to Day 5 or 10 or EOT
Secondary	To evaluate the effect of alvelestat on blood pharmacodynamic markers of Neutrophil Extracellular Trap (NET) activation, elastase, inflammatory and coagulopathy activity	
By treatment group (alvelestat/placebo), change from baseline to Day 5 or 10 in:
 
 • Blood biomarkers of NETosis (cell-free DNA; citrullinated histone H3; Myeloperoxidase (MPO)-DNA complexes) • Blood biomarkers of inflammation (absolute neutrophil count; absolute lymphocyte count; neutrophil-lymphocyte ratio [NLR], C-Reactive protein, procalcitonin) • Pro-inflammatory cytokines IL-1beta, IL-6, IL-8, TNF-alpha) • Coagulopathy as measured by D-Dimer • Plasma desmosine/isodesmosine
	To explore the effect of alvelestat on pulmonary function	
By treatment group (alvelestat/placebo):
 
Proportion of subjects alive and free of respiratory failure (without need for non-invasive or invasive mechanical ventilation, high flow oxygen, or Extracorporeal Membrane Oxygenation (ECMO) at Day 29

	The effect of alvelestat on clinical outcomes	
By treatment group (alvelestat/placebo):
 
 • Mortality rate at Day 90 • Proportion of subjects alive and free of respiratory failure (without need for non-invasive or invasive mechanical

Endpoints	Definitions
	
ventilation, high flow oxygen, or ECMO) at Days 5, 10 and 60
 
 • Length of hospital stay • Length of ICU stay 
Time to room air (those on supplemental oxygen at Baseline)

The effect of alvelestat on disease severity
	
By treatment group (alvelestat/placebo):
 
 • Percentage of patients deteriorating (>1 and >2 increase in WHO 9-point ordinal scale*) at Day 5, Day 10, Day, Day 29 and Day 60 
Percentage of patients improving (>1 and >2 decrease in WHO 9-point ordinal scale) at Day 5, Day 10, Day 29 and Day 60

To explore Pharmacokinetics (PK) in patients with COVID-19
	
Plasma PK (sparse sampling taken pre or 1-2 hours post study drug dosing) in participants randomized to alvelestat.

7 GENERAL STATISTICAL CONSIDERATIONS

7.1 Sample Size

This is a pilot study and it is not powered based on any specific endpoint. Sample size has been set to minimize the number of patients exposed, but still large enough to give reliable estimates on the efficacy and safety of alvelestat in the target population.

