10.0 STATISTICAL CONSIDERATIONS

10.1 Sample Size Determination

Over the course of the study, 15 participants will be randomized in a 2:1 ratio to receive one of the following: alvelestat or placebo on top of SoC or SoC alone .

The primary objective of the study is safety and tolerability. All efficacy analyses are considered exploratory and hypothesis-generating. This is a pilot study and it is not formally powered based on any specific endpoint. Sample size has been set to minimize the number of patients exposed, but still large enough to give adequate safety and tolerability data to support progression of further development, to support estimates on the PK of alvelestat in the target population and to examine for signals on mechanistic and clinical outcome effect.

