7.2 General Principles

This is a double-blind, placebo controlled randomized pilot study which may inform on treatment effect for future studies.

Descriptive statistics

Continuous variables will be summarized using descriptive statistics including number of non-missing observations (n), arithmetic mean (Mean), median (Median), standard deviation (SD), minimum value (Min) and maximum value (Max).

For categorical variables, summaries will include the number of non-missing observations (n) or the number of patients in the population (N) as applicable, the counts of subjects and percentages. Percentages will be rounded to one decimal place.

Statistical Analyses

All analyses are considered exploratory and hypothesis-generating. All tests will be two-sided at 5% significance level. Hypothesis tested for the primary endpoint will be if addition of alvelestat to SoC for up to 10 days will be safe and well tolerated as compared to standard of care plus placebo.

Secondary endpoints are tested independently and there will be no adjustment for multiple tests.

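### SAP 7.1 claims reliable estimates of efficacy and safety, a precision that 15 patients cannot give under either stated allocation

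*SAP*

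**What the plan says.** SAP 7.1 has two parts. It first says "This is a pilot study and it is not powered based on any specific endpoint". It then says the number was kept small to limit exposure but is "still large enough to give reliable estimates on the efficacy and safety of alvelestat in the target population". No effect size, standard deviation, event rate or target interval width is given. SAP 7.2 adds "All analyses are considered exploratory and hypothesis-generating".

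Protocol 10.1 has a parallel passage. It too says "This is a pilot study and it is not formally powered based on any specific endpoint", but its reasons for the size are narrower. On safety the sample is "still large enough to give adequate safety and tolerability data to support progression of further development". On pharmacokinetics it is "to support estimates on the PK of alvelestat in the target population". On efficacy it is only "to examine for signals on mechanistic and clinical outcome effect", and "All efficacy analyses are considered exploratory and hypothesis-generating".

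The documents differ on arm sizes. Protocol 5.2 and 10.1 randomize 15 patients 2:1, 10 to alvelestat and 5 to control. SAP 5.1, 5.4 and 5.5.1 say 1:1, with 7 to 8 per arm in SAP Table 1.

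Where there are no events, SAP 8.3 (composite adverse event endpoint) calls for proportions to be presented. SAP 8.4 and 8.4.2 limit the output to raw proportions if either group has none. SAP Table 8 lists adverse events by number and proportion. No confidence bound is specified for any of these.

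**The concern.** The SAP's preface presents it as describing and expanding on the protocol's statistical content. Here it raises the claim for efficacy from a search for signals to reliable estimates, with nothing to support the change.

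The wording matters for two readings of the results. First, some events of special interest (liver, QTc, neutropenia) may well have zero counts. A table showing 0 of 10 with no bound, under a plan that calls its estimates reliable, invites more reassurance than the data carry. Second, SAP 7.2 says the pilot may inform the treatment effect for later studies, and protocol 3.2 says the mechanistic, safety and PK data will feed progression decisions. A point estimate labelled reliable could be carried forward as an effect size.

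**Working it through.** **The plan's own figure.** The total of 15 cannot be derived, because neither document gives inputs for it. Only the split can be checked: 15 × 2/3 = 10 and 15 × 1/3 = 5, which agrees with protocol 5.2. At 1:1, 15/2 = 7.5, which agrees with 7 to 8 per arm in SAP Table 1.

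**Inputs.** Arm sizes are 10 and 5 (protocol 5.2, 10.1) or 8 and 7 (SAP 5.4). Intervals are two-sided 95% (protocol 10.3). The rates of 5%, 10%, 20%, 50% and 80% below are illustrative assumptions; the documents give none for this purpose.

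**Safety, no events seen.** The exact (Clopper-Pearson) two-sided 95% upper bound is 1 − 0.025^(1/n).
- n = 10: 1 − 0.025^(1/10) = 0.308
- n = 8: 0.369
- n = 7: 0.410

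**Safety, chance of seeing at least one case.** This is 1 − (1 − p)^n.
- n = 10, p = 5%: 1 − 0.95^10 = 0.401
- n = 10, p = 10%: 1 − 0.90^10 = 0.651
- p = 10% with n = 8: 0.570; with n = 7: 0.522

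**Difference in proportions.** SAP 8.4 and 8.4.2 plan a delta-method standard error, so a Wald-type width is the relevant approximation. With a common rate p in both arms, the half-width is 1.96 × √[p(1 − p)(1/n1 + 1/n2)].

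| Arms | 1/n1 + 1/n2 | p = 0.2 or 0.8 | p = 0.5 |
|---|---|---|---|
| 10 v 5 | 0.300 | 1.96 × √(0.16 × 0.300) = 0.429 | 1.96 × √(0.25 × 0.300) = 0.537 |
| 8 v 7 | 0.268 | 1.96 × √(0.16 × 0.268) = 0.406 | 1.96 × √(0.25 × 0.268) = 0.507 |

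The method matters. For an observed 8/10 v 4/5, a difference of zero, the Newcombe interval runs from −35 to +45 points. Its half-width of about 40 points is narrower than the Wald value of 43 at the same rate. Any stated width therefore needs its method and assumed rate beside it.

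**Biomarkers.** SAP 8.4 plans ANCOVA with treatment and one baseline covariate, which leaves 15 − 3 = 12 degrees of freedom. The half-width in residual SD units is t(0.975; 12) × √(1/n1 + 1/n2).
- 10 v 5: 2.179 × √0.300 = 1.19
- 8 v 7: 2.179 × √0.268 = 1.13

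Chance imbalance in the baseline value between arms would widen these slightly.

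**Scale.** A half-width of 20 points at p = 0.5 with 2:1 allocation needs m control patients with 1.96² × 0.25 × 1.5/m = 0.20². This gives m = 36, or about 108 patients in total. This is a yardstick for the word reliable, not a proposed size.

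**The case against.** The case for leaving the clause alone is that its surroundings already disarm it. The sentence before it says the study is unpowered, and SAP 7.2 labels every analysis, safety included, as exploratory. Reliable has no numeric meaning in the documents, so calling it wrong is a judgement. No test, dataset or decision threshold depends on the clause, and deleting it would change no estimate.

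Much of this stands, and it limits the point to one of wording. It does not remove it. A statement about power concerns hypothesis tests, whereas the clause concerns the quality of estimates, which the exploratory label does not withdraw. Intervals of 41 to 54 points either side, or more than one residual SD either side, fit no usual sense of reliable.

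Four stronger readings are tempting, and the documents do not support them.
- A reader might infer that a sample-size calculation is wrong. There is none in either document to be wrong.
- A reader might infer that the protocol makes no comparable claim at all. On safety it does: section 10.1 calls the data adequate to support further development, and section 5.4 regards 15 subjects as suitable for studying safety and tolerability. The clear gap is on efficacy.
- A reader might infer that zero events will be taken as proof of safety. Nothing says so, and neither document sets a numerical go/no-go rule.
- A reader might infer that the trial is too small for its purpose. Looking for signals in an unpowered pilot is compatible with 15 patients.

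**Conclusion.** The point holds as an unsupported claim of precision in SAP 7.1. It is clear for efficacy, where protocol 10.1 speaks only of signals, and a matter of degree for safety, where the protocol says adequate.

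The conclusion is the same under both stated allocations: 8 v 7 narrows the between-arm intervals a little and worsens the zero-event bound for alvelestat. The safety bounds need only the number treated. The proportion widths rest on assumed rates and a Wald approximation. The ANCOVA widths assume all 15 patients contribute; protocol 5.2 does not replace those who discontinue, so losses would widen every interval.

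No planned analysis is invalidated. The correction is still worth making, because it changes what the clinical study report can fairly conclude from a zero count or a point estimate.

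**What to change.** 1. Reconcile the allocation ratio first, between SAP 5.1, 5.4 and 5.5.1 and protocol 5.2 and 10.1. Otherwise any precision statement will contradict one of the documents.

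2. Replace the clause in SAP 7.1 with the protocol 10.1 aim, "to examine for signals on mechanistic and clinical outcome effect", and state that no reliable estimate of efficacy is claimed.

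3. Add the precision for the final arm sizes, with method and assumed rate. Suggested text, using 10 v 5 with the 1:1 values in brackets:

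> If an adverse event is not seen in 10 patients on alvelestat, the exact two-sided 95% upper bound on its rate is 31% [37% for 8 patients, 41% for 7]. An event with an assumed incidence of 10% has a 65% chance of being seen at least once [57% for 8, 52% for 7]. The Wald 95% half-width for a difference in proportions is about 43 points at an assumed rate of 20% or 80% and 54 points at 50% [41 and 51 at 8 v 7]. The ANCOVA 95% half-width is about 1.2 residual SD [1.13 at 8 v 7].

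4. In SAP 8.3 and the clinical study report, give the Clopper-Pearson bound beside each zero-event safety proportion, where the SAP now gives proportions only.

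The cost is one SAP paragraph and one added column in the safety tables. The stated precision becomes less favourable. No extra patients or data are required.

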7.2 General Principles

This is a double-blind, placebo controlled randomized pilot study which may inform on treatment effect for future studies.

Descriptive statistics

Continuous variables will be summarized using descriptive statistics including number of non-missing observations (n), arithmetic mean (Mean), median (Median), standard deviation (SD), minimum value (Min) and maximum value (Max).

For categorical variables, summaries will include the number of non-missing observations (n) or the number of patients in the population (N) as applicable, the counts of subjects and percentages. Percentages will be rounded to one decimal place.

Statistical Analyses

All analyses are considered exploratory and hypothesis-generating. All tests will be two-sided at 5% significance level. Hypothesis tested for the primary endpoint will be if addition of alvelestat to SoC for up to 10 days will be safe and well tolerated as compared to standard of care plus placebo.

Secondary endpoints are tested independently and there will be no adjustment for multiple tests.

7.3 Analysis Populations

Summaries and analysis of safety data will be presented for the Safety Analysis Population. Summaries and analysis of efficacy data will be presented for the intent-to-treat (ITT) population.

- Intent to treat (ITT): Will consist of all randomized patients. Efficacy will be evaluated as randomized.
- Modified intention to treat (mITT): Will consist of randomized participants that have baseline and at least one follow-up assessment available.
- Per protocol population (PP): Will consist of all patients in ITT without any major protocol deviations (determined prior to database lock) deemed to have an effect on efficacy analyses.
- Safety set (SS): Will consist of all randomized and treated patients (at least one dose). Safety will be evaluated by actual treatment.

7.4 Missing Data

All attempts will be made to collect all data per protocol.

- The patients withdrawn from treatment will be followed up regarding their status according to the WHO Ordinal Scale at Day 29 as far as possible (exceptions for patients with withdrawn consent or lost to follow-up) and this data will be the primary source for handling missing data in the study.

Any data point that appears to be erroneous or inexplicable based on clinical judgment will be investigated as a possible outlier.

- If data points are identified as outliers, sensitivity analyses may be performed to examine the impact of including or excluding the outliers. Any substantive differences in these analyses will be reported.

For survival analyses, patients with death as outcome will be censored at Day 29 (Day 60), unless the required event was reached prior to death. Patients who are lost to follow-up or terminate the study prior to Day 29 (Day 60) for other reason than death and prior to observing/experiencing the event will be censored at the time of their last observed assessment. The only time to event analyses is the time to recovery.

For secondary endpoint analyses, the following imputation rules will be used for patients who are lost to follow-up, terminate early from the study, or do not have further outcome data available after discharge for any reason than death:

- Patients with no data collected at the actual time point of interest for other reason than death, the last assessment of their status prior to this time point will be used as a representative for that time point. Especially, if the patient's clinical status scale is 1 or 2 at the last observed assessment, then the patient will be considered to be recovered through Day 29.
- For endpoints assessing total time (oxygen or non-invasive ventilator care), the status for patients with no data collected for other reason than death, will be assumed unchanged from last assessment of the score up to last day in the definition of the endpoint (Day 29). Thus, no extra days will be added for patients without oxygen or patients without non-invasive ventilator care at last assessment.
- Patients that die in the study will be handled as worst case in all the analyses, that is they are considered to be on oxygen need, non-invasive and invasive mechanical ventilator need for all time points following the death.
- In analyses of oxygen need, patients in ventilator care (non-invasive or invasive mechanical) will be considered in oxygen need for the corresponding time period and patients with death as outcome will be considered in oxygen need for the remainder of the time period of evaluation.
- In analyses of non-invasive ventilator need, patients that require invasive mechanical ventilation will be considered also as having a non-invasive ventilator need. Patients with death as an outcome will be considered as having non-invasive ventilator need from time of death for the remainder of the time period of evaluation.

- In analyses of invasive mechanical ventilator need, patients with death as an outcome will be considered in invasive mechanical ventilator need for the remainder of the time period of evaluation
- The change from baseline in the WHO ordinal scale will use the baseline score and the score at the endpoint using imputation for missing data as stated above, that is the last assessment of their status prior to this time point will be used.
- If the patient is discharged and no further hospitalization data are available, then the patient will be assumed to not have been readmitted. Thus, no additional imputed days on hospitalization will be added to the number of days recorded on available assessments for these patients.

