4.0 OBJECTIVES AND ENDPOINTS

Objective	Endpoint
Primary	
By treatment group (alvelestat/placebo):
 
 • Numbers and % of subjects who experience at least 1 treatment-emergent adverse event to Day 60 (Safety Outcome Assessment) • Adverse events of special interest (liver function abnormalities, corrected QT interval, infections, and neutropenia) and clinically significant safety monitoring labs tests to Day 14 (acute treatment period) or EoT • Number and % of subjects that discontinue alvelestat to Day 5 or 10 • Number and % of subjects requiring dose reduction to Day 5 or 10 • Number and % of subjects with AE of headache on prospective questioning and CTCAE severity Grade to Day 5 or 10 • Change in vital signs, EKG, safety laboratory measures to Day 5 or 10 or EOT
Secondary	
By treatment group (alvelestat/placebo), change from baseline to Day 5 or 10 in:
 
 • Blood biomarkers of NETosis (cell-free DNA; citrullinated histone H3; Myeloperoxidase (MPO)-DNA complexes) • Blood biomarkers of inflammation (absolute neutrophil count; absolute lymphocyte count; neutrophil-lymphocyte ratio [NLR], C-Reactive protein, procalcitonin) • Pro-inflammatory cytokines IL-1beta, IL-6, IL-8, TNF-alpha) • Coagulopathy as measured by D-Dimer • Plasma desmosine/isodesmosine

[figure not shown]
Objective	Endpoint

 To explore the effect of alvelestat on pulmonary function 	By treatment group (alvelestat/placebo): 
 Change from baseline to Day 5 or 10, or EoT in SaO₂/FiO₂

 The effect of alvelestat on disease progression 	By treatment group (alvelestat/placebo): 
 Proportion of subjects alive and free of respiratory failure (without need for non-invasive or invasive mechanical ventilation, high flow oxygen, or Extracorporeal Membrane Oxygenation (ECMO) at Day 29

 The effect of alvelestat on clinical outcomes 	By treatment group (alvelestat/placebo): 
 Mortality rate to Day 90 safety endpoint Proportion of subjects alive and free of respiratory failure (without need for non-invasive or invasive mechanical ventilation, high flow oxygen, or ECMO) at Days 5, 10 and 60 Length of hospital stay Length of ICU stay Time to room air (those on supplemental oxygen at Baseline)

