10.3.2 Efficacy Analyses (Secondary Endpoints)

Comparison of alvelestat and placebo will be performed using an analysis of covariance (ANCOVA) model for continuous variables, with Least Squared means for the difference between pairwise treatment regimens, standard errors, two-sided 95% CIs and P-value for the difference between pairwise treatment regimens.

Categorical variable will be compared between treatments by Chi-square test (or Fisher's exact test as appropriate).

Endpoint	Statistical Analysis Methods
Biomarkers	
Within individual absolute and % change from baseline will be calculated. An analysis of covariance (ANCOVA) model with baseline levels as a covariate and treatment strata as factors will be used to generate least squared means and least squared mean differences between treatment groups. Continuous measures will be log transformed where appropriate.
 
The parameters during treatment will be compared to the baseline values for active and placebo patients separately to evaluate natural variability of the markers.
 
The time-matched biomarker values will be compared between placebo and active groups to assess the differences outside natural variability and time to significant change for the responsive biomarkers.

SaO ₂ /FiO ₂	Within individual absolute and % change from baseline will be calculated.
Disease progression (alive and respiratory failure free)	The proportion alive and respiratory failure free will be presented by the number of observations, absolute and relative (%) frequency.

Endpoint	Statistical Analysis Methods
Other clinical outcomes	
Continuous variables (e.g. duration of hospital/ICU stay) mean, standard deviation, minimum, maximum, median, lower quartile, and upper quartile).
 
Change in level of respiratory support will be presented as shift tables.
 
Time to event (e.g. time to room air, to death, to discharge), will be analysed using Kaplan-Meier methods, and quartiles for the median time to event will be presented together with their 95% confidence intervals. Comparisons between treatment regimens will be performed by means of the log-rank test.

Disease severity (WHO 9-point ordinal scale)	
Change from baseline will be presented as mean, standard deviation, minimum, maximum, median, lower quartile, and upper quartile).
 
Responder analyses (improvement and deterioration) will be presented as number of observations, absolute and relative (%) frequency.

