3 PREFACE

The SAP for "A Phase Ib/II, single center, placebo-controlled, randomized, blinded study in adult patients (≥ 18 years) with COVID-19 Respiratory Disease, to evaluate, Safety, Tolerability and mechanistic effect of Alvelestat on top of standard of care (COSTA)" describes and expands upon the statistical information presented in the protocol.

This document describes all planned analyses and provides reasons and justifications for these analyses. It also includes sample tables, listings, and figures planned for the final analyses.

Any deviation from this SAP will be described and justified in protocol amendments and/or in the clinical study report (CSR), as appropriate. The reader of this SAP is encouraged to also review the study protocol for details on conduct of the study and the operational aspects of clinical assessments.

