8.3 Primary Endpoint Analysis

The primary endpoint is safety and tolerability of alvelestat. Safety endpoints include SAEs and AEs. Adverse events will be analyzed using quantitative and qualitative measures.

Treatment-emergent adverse events will be summarized by treatment group for all AEs, related AEs, serious adverse events, deaths, adverse events leading to discontinuation of study medication or to withdrawal from study, adverse events of different severity and adverse events of different chronicity.

Treatment-emergent adverse events will be coded using MedDRA and summarized by system organ class and preferred term for each treatment group.

The time to the composite AE endpoint (death, SAE, severe AE or ET/W of treatment during first 10 days) will be compared between treatment groups using the log-rank test and difference between treatment arms will be expressed as a difference in proportions as measured by the Cochran Mantel-Haenzel (stratum)-weighted estimator based on the fitted logistic regression model

- If '0' events, proportions will be presented.

Summaries of the results of the safety analysis are displayed in **Table 8**.

Table 8. COSTA analysis tables - Safety Analyses.

Table #	Table Name
	Time to first composite AE (Safety Analysis Set)
	Number/Proportion Treatment emergent adverse events summary (Safety Analysis Set)
	Number/Proportion TEAEs leading to discontinuation of study treatment by system organ class and preferred term (Safety Analysis Set)
	Number/Proportion TEAEs with an outcome of death by system organ class and preferred term (Safety Analysis Set)

Deaths, Serious Adverse Events and other Significant Adverse Events

Narratives will be provided for deaths and serious adverse events.

Pregnancies.

For any patients in the Safety population who become pregnant during the study, every attempt will be made to follow these patients to completion of pregnancy to document the outcome, including information regarding any complications with pregnancy and/or delivery.

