- Change from baseline in desmosine/isodesmosine will be compared between treatments using ANCOVA models with treatment allocation as a factor and baseline desmosine/isodesmosine as a covariate. Estimated treatment difference with 95% confidence intervals and associated 2-sided p-value will be given.
- Biomarker values that are below the lower limit of quantitation of assay will be reported as the lower limit of quantitation (LLQ)/2.
- Biomarker values may be log transformed if appropriate.

The proportion of patients with recovery at Day 29 will be compared between treatment groups using a logistic regression model adjusting for treatment and COVID disease severity. The difference between treatment arms will be expressed as a difference in proportions as measured by the Cochran Mantel-Haenzel (stratum)-weighted estimator based on the fitted logistic regression model. The delta method will be used to calculate the standard error for the difference and the associated confidence interval [Ge, 2011]. In addition, the raw proportions per treatment group will be given. If 0 events in any of the groups only raw proportions will be given.

Summaries of the results of the secondary analysis for recovery are displayed in Table 10.

Table 10. COSTA analysis tables – Secondary Analysis (Recovery)

Table #	Table Name	Table Contents
	Proportion of Patients with Recovery at 29 Days, ITT	Overall and by Treatment Group 
 • By Age Group • By Sex • By COVID Disease Severity
	Proportion of Patients with Recovery at 29 Days, PP	Overall and by Treatment Group

Patients that die in the study will be handled as worst case in all analyses.

To have an evaluation using all patients we will count an event as the type of need or worse (e.g., patients with oxygen need; non-invasive ventilator need; ventilator need; or with death at time of evaluation will be counted as having data supporting oxygen need), and included in both denominator and numerator.

8.4.1 Time to a recovery state (Day 1 - Day 29; measured in days)

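### The SAP tests recovery, an outcome that neither document lists, as its only time-to-event analysis, while time to room air and ICU stay have no planned analysis

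*SAP*

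**What the plan says.** Protocol section 4.0 lists length of hospital stay, "Length of ICU stay" and time to room air among the secondary clinical outcomes. Protocol 10.3.2 gives the methods. "Time to event (e.g. time to room air, to death, to discharge), will be analysed using Kaplan-Meier methods", with log-rank comparisons between arms. Stays are summarised descriptively: "Continuous variables (e.g. duration of hospital/ICU stay) mean, standard deviation" and so on. The protocol has no recovery endpoint.

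SAP section 3 sets its own scope: "This document describes all planned analyses and provides reasons and justifications for these analyses". SAP Table 3 (section 6.2) keeps ICU stay and "Time to room air (those on supplemental oxygen at Baseline"), and does not list recovery. SAP 8.4 then states: "The proportion of patients with recovery at Day 29 will be compared between treatment groups using a logistic regression model". Section 8.4.1 adds a log-rank test of time to recovery, 8.4.2 adds the Day 60 proportion, and Figure 2 in Table 12 is a Kaplan-Meier plot of recovery. In SAP 7.4, the paragraph on censoring ends: "The only time to event analyses is the time to recovery".

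**The concern.** A SAP should give each listed endpoint a method and should mark anything added to the list. Here an outcome on neither list receives a logistic model, a log-rank test, its own Table 10 (with displays by age, sex and severity, and a per-protocol version) and a figure. Two outcomes on both lists receive nothing in section 8, and an explicit sentence appears to exclude one of them.

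An analyst who follows the SAP will produce recovery results and no result for time to room air or ICU stay. An analyst who follows the protocol will produce different outputs. Population, censoring and the handling of deaths for the missing analyses would then be settled late. Protocol 7.3 keeps the sponsor and principal investigator blinded only until the Day 60 assessment, so an analysis specified after that could be chosen with the allocation known.

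**Working it through.** No arithmetic applies: the study is not powered on any endpoint, and the point rests on no sample size, event count or error rate. The check traces each outcome through both documents.

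| Outcome | Protocol 4.0 | Protocol 10.3.2 | SAP Table 3 | SAP section 8 |
|---|---|---|---|---|
| Time to room air | listed | Kaplan-Meier, log-rank | listed | none |
| Length of ICU stay | listed | descriptive | listed | none |
| Length of hospital stay | listed | descriptive | listed | 8.4.6, Wilcoxon |
| Time to death | mortality to Day 90 | Kaplan-Meier, log-rank | mortality at Day 90 | proportions only |
| Time to discharge | not listed as such | Kaplan-Meier, log-rank | not listed (defined in Table 2) | no time-to-event analysis |
| Recovery | absent | absent | absent | 8.4, 8.4.1, 8.4.2, Tables 10 and 11, Figure 2 |
| Procalcitonin | listed | biomarker ANCOVA | listed | not in Table 9 |

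**Definition of recovery.** SAP Table 2 defines discharge, improvement and worsening, but not recovery. The nearest thing is an imputation rule in 7.4, under which a patient whose last WHO score is 1 or 2 counts as recovered through Day 29. Table 2 uses the same two scores to date discharge. Neither place says what happens at score 0.

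**What the 7.4 sentence displaces.** Read against protocol 10.3.2, it displaces three analyses: time to room air, time to death and time to discharge. It does not displace ICU stay, which the protocol treats as a continuous variable. The ICU gap arises because 8.4 and Table 11 do not mention it.

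**Consistency inside the SAP.** Section 8.3 says the time to a composite adverse event "will be compared between treatment groups using the log-rank test", and section 7.6 gives that analysis its own censoring rule. The sentence is therefore false as worded and can stand only if limited to efficacy.

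**Whether another analysis covers time to room air.** SAP 8.4.4 sums all days on oxygen between Day 1 and Day 29, consecutive or not, counts patients never on oxygen as 0 days, and compares arms by Wilcoxon. The listed endpoint is the time to one event, in patients on oxygen at baseline. Population, outcome and test all differ. The proportions on oxygen at Days 10 and 29 in 8.4.2 are snapshots and do not supply it either.

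**The case against.** The best defence has five parts.

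- **All of this is exploratory.** Both documents say so, the primary objective is safety, and protocol 3.2 bases progression decisions on mechanistic, safety and PK data. This limits the consequence. It does not explain why listed endpoints lack a method while an unlisted one has several outputs with tests.
- **The protocol still supplies the methods.** The SAP describes itself as expanding on the protocol, and its section 10 permits extra tables. That is a fair reason not to call the endpoints abandoned. But the SAP also claims to cover all planned analyses, and the 7.4 sentence is an explicit exclusion, so the two documents have to be reconciled.
- **Recovery may be discharge under another name.** If recovery means score 1 or 2, time to recovery would approximate time to discharge, which protocol 10.3.2 names. This is plausible and would narrow the gap for that one analysis. The SAP does not say it.
- **The 7.4 sentence is about efficacy.** Its paragraph concerns Day 29 and Day 60 censoring, and safety has its own rule. On that reading the conflict with 8.3 disappears, but the conflict with protocol 10.3.2 does not.
- **Procalcitonin may be covered.** The ANCOVA text for inflammatory markers gives CRP only as an example, and Figure 1 covers each biomarker. This stands, so the Table 9 omission is minor.

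A reader might also infer outcome switching, or that recovery has been made the headline clinical result. The documents do not support either. Both omitted endpoints remain in SAP Table 3, recovery is labelled secondary and follows the biomarkers, the SAP does not rank its efficacy endpoints, and no registry record is available to compare against.

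**Conclusion.** The point holds as an inconsistency that changes what would be reported. Its size is two protocol-listed secondary endpoints with no analysis in SAP section 8, three time-to-event analyses named in protocol 10.3.2 and displaced by one sentence, and one unlisted, undefined outcome that is tested. The result is a risk of selective reporting, not evidence of it, and the primary safety objective does not depend on it. The conclusion assumes that the SAP is followed as written and that its claim to completeness is meant. If the protocol's methods are intended to apply wherever the SAP is silent, the gap for ICU stay closes, but the 7.4 sentence still has to be corrected and recovery still needs a definition.

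**What to change.** - Delete the 7.4 sentence, or replace it with a correct list of the time-to-event analyses, separating efficacy from safety.
- Add the Kaplan-Meier and log-rank analysis of time to room air, restricted to patients on oxygen at baseline. The existing 7.4 rule (deaths before the event censored at Day 29 or Day 60) can be used; state which horizon applies and how patients discharged on oxygen are handled.
- Add the protocol's analyses of time to discharge and time to death. The 7.4 rule for deaths cannot serve the latter, where death is the event, so state the follow-up horizon and the censoring of survivors.
- Add the protocol's descriptive summary of ICU stay to Table 11.
- Define recovery explicitly in Table 2, stating whether score 0 counts and how it differs from discharge, and label it as additional to the protocol endpoints. Dropping its subgroup displays is optional.
- Minor: add procalcitonin to Table 9 so that it matches Table 3.

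The cost is SAP text and a few tables. Protocol 9.3 already records daily respiratory support and the dates of hospital and ICU admission and discharge and of death. The changes should be made before unblinding.
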